#### **4. Study Endpoints**

**Primary Endpoint:** decrease in impulsivity and compulsion (as measured by change in NIH Examiner Score) with active tDCS compared to sham

**Secondary Endpoint:** change in weight over the study period

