## 6. Study Methods, Procedures, and Statistical Plan

### Study Design:

For this single-site pilot study our statistical approach will be similar to prior work done by members of our team previously, a double-blind, randomized controlled design with participants randomized to either active or sham tDCS. For this study Veterans will be referred as potential candidates because they have obesity and self-report that they tend to have at least one occasion of out-of-control eating per week on average. Participants will be trained on the Brain HQ, an interactive computer software package in which subjects work through a series of structured exercises designed to stimulate neuroplasticity. Participants will be randomly assigned to receive either active tDCS or sham stimulation with their training during one hour session each day( 13 minutes of stimulation , 20 minute stimulation break, followed by 13 more minutes of stimulation) over five days. A 2 mA current will be applied with two 25 cm^2 saline soaked electrode sponges with anode at F4 (right) and cathode at F3 (left) concurrent with the Brain HQ. To evaluate generalization, an untrained NIH Examiner Battery sub-set testing 4 modalities of executive function will be performed before and after the five days of training. Subjects will then go through the Move Mass Behavior Modification after completing the five days of treatment. (This 16-week structured behavior modification program of bi-weekly sessions is usual care for these participants.) Participants will return for the trained and untrained testing at V7 (halfway through the behavior modification course) and V8 (final study visit to occur after the behavior modification course) follow-up sessions without stimulation. For the trained Brain HQ tasks, growth curve analysis (GCA) examining individual variation of the

growth rates over time will be done (across the 5 days of tDCS sessions and the subsequent follow-ups) to examine for change in individual and group trajectories over time. For the untrained NIH Examiner tasks, GCA will be used to evaluate for individual and group effects in executive function in the four domains of the NIH Examiner Battery from pre- to post-treatment and through follow-up sessions. We will also compare pre- and post- treatment results in the cravings and binging questionnaires within and between groups.

Figure 1: Study Visit Schedule

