#### ***tDCS session visits (V2-6):***

Subjects will go to the Minneapolis VAMC GRECC where they will undergo the tDCS sessions. Subjects will be randomly assigned to active vs. sham treatments which will occur on 5 sequential weekdays. The tDCS session will include a pre/post symptom rating questionnaire, 13 minutes of stimulation, a 20-minute stimulation break, followed by 13 more minutes of stimulation. Subjects will complete the Brain HQ test during stimulation and the stimulation break. The final stimulation visit, V6 will include NIH Examiner and their weight will be collected. These sessions will last around 1 hour to 1.5 hours each.

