### **Statistical Plan and Power Analysis**

For this pilot study our statistical approach will be similar to prior work done by members of our team, a randomized controlled design with participants randomized to either active or sham tDCS.

Power Analysis. For Aim 1, the primary comparison will be difference in change before and after training on untrained impulsivity-related tests of executive functioning between active and sham tDCS. [name] and colleagues' preliminary data found an effect size of  $d=.97$  between active and sham tDCS groups. Based on these results, the current pilot project is powered to detect an effect size of .97 with 80% power and an alpha = .05 (N = 20). Power to detect a medium effect size will be approximately .60. Thus, this study is well-powered to detect changes on the primary cognitive outcome variables.

For the secondary aim of weight loss, an ANOVA will be used with weight as the dependent variable and the grouping variable will be active vs. sham. We will be testing for a Group x Time interaction for weight.

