## **14. Data Management**

Data Analysis Plan: For this pilot study participants will be randomized to either active or sham tDCS. For the trained task, growth curve analysis (GCA) examining individual variation of the growth rates over time will be done (across all 10 tDCS sessions and the subsequent follow-ups) to examine for change in individual trajectories over time. For the untrained task (NIH Examiner), GCA to evaluate for enhancement of executive function in the four domains from pre- to post-treatment as compared with the sham group will be analyzed. As a secondary aim we will evaluate weight loss response during and after the behavior modification program

and evaluate the effect of active vs. sham treatment on weight loss. Results from this study will inform larger follow up studies supported by external applications.

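### Aim 1 has no single defined primary outcome: the score, the tests and the time point differ between sections, and no multiplicity rule or growth-curve term is given

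*Combined protocol and SAP*

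**What the plan says.** The statements that bear on the primary outcome, all in the combined protocol and SAP, are these.

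- **Objectives and Specific Aims.** Aim 1 covers both impulsivity and compulsivity.
- **Study Endpoints.** One measure stands for both constructs: "as measured by change in NIH Examiner Score". How that score is formed is not given.
- **Section 6, Study Design.** "GCA will be used to evaluate for individual and group effects in executive function in the four domains of the NIH Examiner Battery", and this runs "from pre- to post-treatment and through follow-up sessions". The same section has the battery "testing 4 modalities of executive function will be performed before and after the five days of training".
- **tDCS session visits.** "The final stimulation visit, V6 will include NIH Examiner", which fixes the first post-treatment measurement at V6.
- **Section 6, untrained tests.** Four components are described. Low Flanker scores are linked to poor impulse control and low Set Shifting scores to compulsivity. Neither is made primary. Here the battery is placed on either side of the weight-loss programme and at the start and end of the study.
- **Study Procedures.** The Examiner is repeated at V6, V7 and V8, and the Binge Eating Scale (BES) is itself called an impulsivity questionnaire.
- **Statistical Plan and Power Analysis.** For Aim 1, "the primary comparison will be difference in change before and after training on untrained impulsivity-related tests of executive functioning", active against sham. The study is "powered to detect an effect size of .97 with 80% power and an alpha = .05", and a closing sentence speaks of primary cognitive outcome variables in the plural. Compulsivity is not named.
- **Section 14, Data Management.** "GCA to evaluate for enhancement of executive function in the four domains from pre- to post-treatment as compared with the sham group". Follow-up is not mentioned for the Examiner.

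The only model term named for any outcome is Group x Time, and it is named for weight.

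**The concern.** A reader cannot tell which result decides Aim 1. It could be one combined score, any of four domain scores, Flanker alone, Flanker with Set Shifting, or the whole battery read as impulsivity-related. The Abstract's link between impulsivity and poor executive functioning makes that last reading fair. The decisive change could be to V6, to the end of the programme, or a trajectory over all visits.

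With these choices open, the same 20 participants could support different conclusions about Aim 1, and the stated alpha of .05 is not tied to any one of them. Section 14 says the results will inform larger studies, so the headline result should be one pre-specified quantity with a known error rate.

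**Working it through.** **1. The plan's own figure.** Inputs from the Study Summary and the power section: 10 per arm, d = .97, alpha .05, stated power 80%. Two-sided t test on change, df = 18: noncentrality = .97 × √(10/2) = 2.169, critical value 2.101, power **53.7%**. The stated 80% is not reproduced. That is a separate matter and the present point does not depend on it. The 53.7% is used below as the single-test reference.

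**2. False-positive risk if any domain can count as success.** Assumption: k domains, each tested at two-sided .05, no true effect.
- Independent domains: 1 − (1 − .05)^k. For k = 2, 1 − .9025 = 9.75%. For k = 4, 1 − .8145 = 18.5%.
- Correlated domains (simulated two-sample t tests, 10 per arm, k = 4): about 17.5% at correlation .3, 16% at .5 and 13% at .7.
- Counting only results that favour tDCS: about 10% at correlation 0 down to 7% at .7, against 2.5% for one test.

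The documents give no inter-domain correlation, so 0 to .7 is an assumed range.

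**3. Dependence on the GCA term (illustration only).** Assumptions: Examiner at weeks 0, 1, 9 and 17, compound symmetry, d = .97 standardised by the SD of the V6 change, and a benefit fully sustained after V6, shape s = (0, 1, 1, 1). For contrast weights w, effective d = .97 × (w·s)/√(w·w/2), tested with df = 18.
- V6 change, w = (−1, 1, 0, 0): .97 × 1/1 = .97, power 54%.
- Linear slope, w = (−6.75, −5.75, 2.25, 10.25): .97 × 6.75/√(188.75/2) = .674, power 30%.
- Step from baseline to the mean of all later visits, w = (−1, ⅓, ⅓, ⅓): .97 × 1/√(1.333/2) = 1.188, power 71%.

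These values move with the assumptions. An added random-slope SD of .1 residual SD per week lowers the slope to 13% and the step to 51%. If instead the benefit fades to zero by V8, s = (0, 1, .5, 0), under compound symmetry the step falls to 24%. The slope contrast then has w·s = −5.75 + 1.125 = −4.625, so it points against tDCS.

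**4. What each remedy costs in power (10 per arm, unadjusted t test on change).**
- Holm over two domains: the first step uses .025, critical value 2.445, power **41.2%** per test at d = .97. The second step can only add to this.
- Equal-weight composite of four, with only two domains at d = .97 and correlation r: composite d = .97 × (2/4)/√((1 + 3r)/4) = .97/√(1 + 3r). For r = 0, .3, .5 and .7 this is .970, .704, .613 and .551, with power 54%, 32%, 25% and 21%.

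**The case against.** Much of this can be read as loose wording. The Examiner score in the endpoint section may be shorthand for the four components described later. Section 14 may simply be a shorter restatement of Study Design. The power section does state its contrast in words. The study calls itself a pilot, where formal multiplicity control is not always expected. Replacing the GCA would also go beyond what is needed, since stating the tested term would do.

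Some of that stands. Three stronger inferences are not supported:

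- **That the power section drops compulsivity.** Its sentence is introduced as being for Aim 1, and Aim 1 includes compulsivity. The construct is left unnamed, not clearly removed.
- **That the plan promises one test and then runs four.** The power section itself speaks of tests and outcome variables in the plural. It gives one alpha for a power calculation, not one decision rule.
- **That the plan will claim success on any domain.** No section says so, and none rules it out, so the 13% to 19% is conditional.

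What does not stand is the view that nothing needs settling. Even on the generous reading, four components are analysed and nothing says how they combine or which of them decides. Pilot status bears on severity. It does not remove the gap, because the plan states an alpha and a power and calls itself well powered.

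**Conclusion.** The point holds as an inconsistency with missing error control, and the plan should correct it. Confidence is high for that part only. The sections differ on the score, the number of tests and the time point. None supplies a composite, hierarchy, multiplicity rule or GCA term for Aim 1.

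The false-positive range rests on the any-of-four rule and on the assumed correlations. For the GCA, the firm conclusion is only that power, and for a linear slope even the direction, depends on a term left open. The individual percentages depend on assumed visit weeks, covariance and effect shape. A reader might infer that bringing in follow-up visits necessarily costs or gains power; the calculations show that it can do either.

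V6 is the best-supported primary time point (power section, Study Design, session visits). The untrained-tests section points elsewhere, so it must be reconciled too.

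**What to change.** Before unblinding, state one primary contrast: active minus sham at V6, adjusted for the pre-treatment Examiner score. Apply it to one of the following:

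- (i) one composite of the four components, with its scoring written out, at two-sided .05; or
- (ii) Flanker for impulsivity and Set Shifting for compulsivity, with Holm at overall two-sided .05.

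Make the remaining domains, V7, V8 and the BES secondary. The GCA may stay as the model if its time coding and the term that tests the V6 contrast are stated. Otherwise make it supportive. Align Objectives and Specific Aims, Study Endpoints, Study Design, Study Procedures, the untrained-tests text, the power section and section 14.

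The change needs no new data or visits. Option (ii) gives up about 13 percentage points of first-step power per test. Option (i) avoids that, but loses power if only some domains respond, and its scoring has still to be written because the documents do not give it. Baseline adjustment may recover some power. How much depends on the pre-post correlation and on whether d = .97 is scaled by the SD of change or of the raw score, which the power section does not say. Over assumed correlations of .3 to .8, single-test power falls from about 69% to 56% on the first scaling and rises from about 58% to 93% on the second, so no gain should be promised.

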**Study Subjects:**

Potential subjects identified at the Minneapolis VAMC's MOVE Mass Medical Weight Management Clinic where Drs. [name] and [name] attend will be recruited into this 18-week clinical intervention using tDCS. The MOVE Mass Clinic at Minneapolis has a long history, having been established more than 30 years ago and having served as a prototype for the MOVE National Program. Flyers and/or posters will be posted throughout the Minneapolis VA facility and study staff will also present the study to other VA staff during team meetings and via emails to clinicians regarding recruitment. Letters may also be sent out to potential research patients.

Inclusion criteria:

Obese (BMI>30)

Adults, ages 18 years or older

Able to understand English, self-consent and follow study-related procedures

Willing to use a reliable form of birth control if they are of females of child-bearing potential

Exclusion criteria:

History of any of the following: seizures, severe or moderate head injury, head surgery, significant neurological disorder(significance based on Principal Investigator's judgment), frequent severe headaches, history of scalp conditions such as eczema or seborrheic dermatitis, metal in head (other than in mouth) including shrapnel/surgical clips/welding fragments, implanted medical devices (including pumps and cardiac pacemakers), pregnancy, active substance abuse, psychological or medical disorders requiring inpatient treatment, presence of a known metabolic or hormonal disorder (such as Cushing's) which affects weight. History of hypothyroidism is acceptable if subject is on treatment with normal TSH and FT4 on most recent check within the last 3 months and has been on stable dosage of l-thyroxine for at least 3 months, taking it as prescribed.

Subjects will be allowed to participate in the study if they are on obesity medications. It is recommended that patients do not adjust obesity medications once they have enrolled in the study, but if they need to stop or adjust medications due side effects, it will be documented on a medication review form that will be collected at each visit.

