#### ***Visits post tDCS intervention (V7 and V8):***

These visits will be identical to V1 with the exceptions that the history and physical, MN-BEST and blood draw will not be repeated; a weight measurement will be taken along with completion of the BES questionnaire, the Brain HQ and NIH Examiner. A short blinding questionnaire will be asked at V8 to assess the adequacy of tDCS blinding.

Table 1. Table of Assessments

Visit	Assessments	Stimulation	Duration	Compensation
Visit 1	HIPAA, Consent, NIH Examiner, BES, PHQ-9, Medication Review, MN-BEST, Blood Draw, Physical (Weight Measurement), Pregnancy Test (if applicable)	None	120 minutes	\$30
Visit 2-5	tDCS, Pre/Post SRQ, Brain HQ, Medication Review	tDCS	60 minutes	\$15
Visit 6	tDCS, Pre/Post SRQ, Brain HQ, NIH Examiner, Medication Review, Weight Measurement	tDCS	90 minutes	\$22.50
Visit 7-8 (follow-ups)	NIH Examiner, Medication Review, Brain HQ, BES, Weight Measurement, Visit 8 only: PHQ-9, Blinding Questionnaire	None	120 minutes	\$30
Total:			11.5 hours	\$ 172.50

tDCS Device: We will use the Neuroelectrics Starstim system, a wireless multichannel transcranial current stimulator. Periods of tDCS stimulation of 13 minutes will be twice a day, separated by 20 minutes, for five consecutive days (5 total tDCS stimulation sessions). Active tDCS: A 2-mA current will be administered via two circular carbon rubber core electrodes in saline-soaked surface sponges (25 cm^2), placed in a neoprene headcap with marked locations based on the 10-10 EEG system. The anodal stimulating electrode will be at location F4, over right dorsolateral prefrontal cortex (DLPFC) and cathodal electrode at location F3, over left DLPFC. This tDCS configuration has been shown to be effective for stimulating DLPFC. Sham tDCS: For sham stimulation, the electrodes will be placed at the same positions as for active stimulation (F3 and F4), but current will be ramped down immediately after the initial 30 s ramp up period. Thus, participants will feel the initial itching sensation associated with tDCS but will receive no active current for the rest of the stimulation period. This method of sham stimulation has been shown to be reliable (Gandiga, Hummel, & Cohen, 2006). The Starstim software supports the measurement of electrode impedance. Before each training session, the impedance of the electrodes will be checked and verified to be ≤10 KOhm. During a training

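### The weight analysis uses neither baseline obesity medication nor baseline weight as a covariate, although both are recorded; with 10 per arm this can cost precision and leave the estimate open to chance imbalance

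*Combined protocol and SAP*

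**What the plan says.** Section 6, Study Subjects, admits users: "Subjects will be allowed to participate in the study if they are on obesity medications". On later changes it says "It is recommended that patients do not adjust obesity medications once they have enrolled in the study"; if side effects force a stop or adjustment, "it will be documented on a medication review form that will be collected at each visit". No period of unchanged use before entry is stated.

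Table 1 lists a medication review at every visit, V1 included. Weight is taken at V1, V6, V7 and V8; the row for the last two reads "NIH Examiner, Medication Review, Brain HQ, BES, Weight Measurement".

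The secondary endpoint in Study Endpoints is "change in weight over the study period". Under Statistical Plan and Power Analysis, "an ANOVA will be used with weight as the dependent variable and the grouping variable will be active vs. sham", followed by "We will be testing for a Group x Time interaction for weight". Section 14 (Data Management) adds only that the team will look at weight loss during and after the programme "and evaluate the effect of active vs. sham treatment on weight loss". Neither section uses medication as a covariate, subgroup or sensitivity variable. The Study Summary gives 10 per arm, and no stratification or minimisation is described.

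**The concern.** Obesity medication is meant to change weight, so whether a person takes it at entry is a natural candidate predictor of the Aim 2 outcome. It is known before stimulation starts and is already being collected. A model with only arm and time leaves any variation in weight change due to medication in the error term. With 10 per arm and nothing in the design to balance users, the arms may also differ noticeably in the number of users. At stake are the precision of the weight estimate and how it can be read if the arms turn out unequal. Section 14 says the results will inform larger studies, so the weight estimate may be carried forward.

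**Working it through.** **The plan's own figure.** There is none for weight: no SD, effect size or power. The stated N = 20 (d = .97, 80% power, alpha .05) concerns the cognitive outcome. A two-sided t test with 10 per arm gives power .54 for d = .97, so that statement does not reproduce. That is a separate matter, and nothing below depends on it.

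**Inputs.** From the documents: 10 per arm, no stratification described, weight model with arm and time only. Assumed: 8 (or 4) of 20 on medication, residual SD of weight change 4 kg, true arm difference 4 kg, and an effect of medication on weight *change* of 0 to 7 kg.

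**Step 1, error variance.** If a share p uses medication and it shifts weight change by g residual SDs, leaving it out multiplies the variance by 1 + p(1 − p)g².
- p = .4, 3 kg (g = .75): 1 + .24 × .5625 = 1.135
- p = .4, 5 kg (g = 1.25): 1 + .24 × 1.5625 = 1.375
- p = .2, 5 kg: 1 + .16 × 1.5625 = 1.25

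Over p = .2 to .5 and g = .5 to 1.5, the inflation runs from 4% to 56%.

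**Step 2, power with the medication covariate alone.** Simulated trials, least squares on weight change, two-sided alpha .05, simulation error about .01. As a check, the unadjusted case with no medication effect has d = 4/4 = 1, noncentrality √(10/2) = 2.236 and 18 df, giving .56.

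| Users of 20 | Medication effect | Unadjusted | Adjusted |
|---|---|---|---|
| 8 | 0 kg | .57 | .55 |
| 8 | 3 kg | .52 | .55 |
| 8 | 5 kg | .44 | .54 |
| 8 | 7 kg | .35 | .53 |
| 4 | 3 kg | .53 | .54 |
| 4 | 5 kg | .47 | .53 |

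Break-even is near 2 kg, or 0.5 residual SD (.54 and .54 with 8 users).

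**Step 3, cost of two covariates.** Residual df fall from 18 to 16, and the critical t rises from 2.101 through 2.110 to 2.120. With medication and a baseline covariate that are both unrelated to weight change, power falls from about .57 to .52. With 8 users, a 3 kg medication effect and an uninformative baseline covariate, there is no net gain (.51 and .51).

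**Step 4, chance imbalance.** With 8 users among 20 and 10 per arm, the hypergeometric probability that the arms differ by 4 or more users is .170. With 4 users it is .087. A 6-versus-2 split at 5 kg per user shifts the contrast by (.6 − .2) × 5 = 2 kg, half the assumed arm difference. Given that split and no true effect, the unadjusted false-positive rate is about .11 to .12; adjusted, it is .05.

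**Step 5, what the covariate must look like.** The Group x Time test works on within-person differences. A term βM that is constant over time cancels from W(V8) − W(V1), whereas a term γ(t)M leaves (γ(V8) − γ(V1))M. In a simulated data set of 20 people at 4 times, the interaction F was 2.814 without medication, 2.814 with a medication main effect and 1.619 with medication by time. V1 weight is itself one of the outcome times in that model, so it cannot simply be added there as a covariate.

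**The case against.** The strongest reply is that randomisation already deals with this. Over repeated trials, chance imbalance is part of the unadjusted standard error and the type I error stays at alpha. That stands. A reader might infer that the planned comparison is biased or its test invalid, and the documents do not support that. The .11 to .12 rate above is conditional on one particular split.

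A reader might also infer that medication is a strong known source of weight change in this trial. The documents give no figure for it. Participants are advised not to change medication, and a long-term user's lower weight *level* cancels in the Group x Time test. Only an effect on *change* after V1 matters, and a yes/no at V1 mixes recent starters with long-term users, so 5 to 7 kg may be too large for this variable. This limits the size of the point but does not remove it.

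Third, covariates are not free at N = 20, and the endpoint is secondary in a pilot with no power claim for weight. Both are true. Against that, adding covariates after the weights have been seen would be open to selective choice, so the decision belongs in the plan.

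**Conclusion.** The concern holds as a matter of precision and conditional balance for Aim 2. The documents establish that obesity medication is allowed, that medication and weight are recorded at V1, and that the weight analysis uses neither as a baseline covariate.

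The size is not established. Under the assumptions above, adjusting for medication alone loses about 2 to 3 points of power if medication is irrelevant and breaks even near 0.5 residual SD. With 8 users it gains about 10 points at 5 kg and 18 at 7 kg; with 4 users it gains about 6 at 5 kg. Even adjusted, power stays at about .53 to .55, so the change does not make the weight comparison well powered. It is a worthwhile, inexpensive improvement to a secondary pilot analysis, and the primary aim is untouched.

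**What to change.** In Statistical Plan and Power Analysis, name one weight analysis, in either of two forms:

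- ANCOVA of change in weight from V1 to V8 on arm, V1 weight and V1 obesity-medication use (yes/no); or
- the repeated-measures model with a medication-by-time term added. A medication main effect alone would change nothing in the test of interest.

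Study Procedures lets baseline items slip to V2, so define both baseline values as those recorded before the first stimulation.

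Do not adjust for medication changes after randomisation, since treatment may influence them; report them by arm. Label any analysis that drops weights taken after a change as exploratory, because it selects on a post-randomisation event.

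No new data are needed, provided the V1 review records obesity medication in use. The ANCOVA costs two degrees of freedom: about 5 points of power if neither covariate is prognostic, or 2 to 3 for medication alone. A V1-to-V8 change also sets the V6 and V7 weights aside, which the repeated-measures form keeps.
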